#### **16.1.4 Study Files and Retention of Records**

The investigator must retain all study records until at least 2 years after the last approval of a marketing application in an ICH region and until there are no pending or contemplated marketing applications in an ICH region or at least 2 years have elapsed since the formal discontinuation of clinical development of the investigational product as per 21 CFR 312.62 and ICH GCP E6 4.9.5 and 5.5.12. These documents must be retained for a longer period, however, if required by the applicable regulatory requirements or by an agreement with

Allos. It is the responsibility of the sponsor to inform the investigator as to when these documents no longer need to be retained. If the investigator relocates, or for any reason desires to dispose of the records, the study records may be transferred to another institution, another investigator, or to the sponsor upon written agreement between the investigator and the sponsor.

## **16.2 Recording and Collecting of Data**

In accordance with ICH and GCP guidelines, the investigator will maintain complete, accurate, legible, and easily retrievable data, and will allow personnel authorized by Allos access to all study data at any time. Such data shall also be secured in order to prevent loss of data.

### **16.2.1 Case Report Forms**

Allos may make use of electronic data capture (EDC) or paper CRFs.

When using paper, Allos' CRFs are printed on no carbon-required paper to permit multiple copies. The investigator will retain the bottom copy for his/her study files. Data collected for each patient will be recorded on the CRFs. The investigator is responsible for ensuring that all data submitted are true, accurate, and ultimately complete.

Completed CRFs will be reviewed and signed by an investigator listed on the US Form FDA 1572 or equivalent. The CRA will verify the CRF data with the patient's source data, evaluate the data for accuracy, consistency, and completeness, and will ensure that all forms with missing data and/or errors are ultimately addressed.

When using EDC, data collected for each patient will be entered by site staff into an EDC database. The investigator is responsible for ensuring that all data submitted are true, accurate, and ultimately complete.

Completed, EDC data will be reviewed by an investigator listed on the US Form FDA 1572 or equivalent. This review will be documented by the investigator or equivalent logging into the EDC database and providing sign off using his/her 21 CFR Part 11 compliant electronic signature. The CRA will verify the CRF data with the patient's source data, evaluate the data for accuracy, consistency, and completeness, and will ensure that all screens with missing data and/or errors are ultimately addressed.

Accurate and complete CRFs for a patient, either via paper or EDC, must be submitted to Allos in a timely manner.

### **16.2.2 Data Clarification Forms**

Data Clarification Forms (DCFs), such as Queries, Site Notifications, and CRA Addenda, will be used by Allos staff or designee to attempt to correct or clarify missing, incomplete, or illogical data. Queries and Site Notification may be completed individually by an appropriate person on the Delegation of Authority form, but must be reviewed, and the

tracking coversheet signed by, an investigator listed on the US Form FDA 1572 or equivalent. CRA Addenda may be completed by the CRA but must be reviewed and signed by an investigator listed on the US Form FDA 1572 or equivalent.

For EDC studies, this process is performed electronically.

### 16.2.3 Self-evident Corrections

CRF data are expected to be accurate, consistent, and complete. Allos Clinical Data Management department or designee (eg, a clinical research organization [CRO]) may apply the following conventions to correct the Allos database without issuing a DCF to site staff. However, a DCF may still be generated as needed for clarification/confirmation.

- Header data will be corrected if the error is obvious and a correction is supported by the remainder of the CRFs.
- Duplicate data will be deleted unless the CRF specifically allows for repeat values. For example, if identical lab values (including date and time, if applicable) are recorded for a protocol-specified visit and for a miscellaneous/unscheduled visit, only the protocol specified visit data will be entered in the database.
- Data recorded within the casebook can be moved to the appropriate CRF field if no data are changed.
- Relevant comments or marginalia will be added to the Comments section.
- Misspellings may be corrected only if the correction clarifies (eg, enables coding), but does not change, the meaning or contextual use of the word.
- Long text fields will be shortened, if needed, using generally accepted abbreviations that do not change the clinical meaning of the text.
- Dates (eg, year boundary, day/month inversion) will be corrected if the change is supported by the remainder of the CRFs.
- Only the Stop Date will be recorded if a Stop Date and “Continuing” (or similar) are provided.
- An indicator field left blank or marked “no” (eg, AEs present?) will be updated to “yes” if data are present.
- If a field where “If Other, specify” (or similar situation) includes data but the box is blank (or similar), the box will be checked for the database.
- If the resolution area of a Site Notification (SN) is blank but the SN is signed, the response from the site will be interpreted as “Agree”.

### 16.2.4 Drug Accountability

In accordance with all applicable regulatory requirements, the investigator or designated site staff must maintain pralatrexate accountability records throughout the course of the study. This person(s) will document the amount of pralatrexate administered to patients. The CRA will review inventory and accountability documentation during monitoring visits.

The investigator will not supply investigational study drug to other investigators not listed on the US Form FDA 1572 or equivalent. Investigational study drug use, other than as directed by this protocol, is not allowed without prior authorization from Allos.

All unused vials of pralatrexate must be accounted for at the site and maintained in a secured, locked storage area with access limited to authorized study personnel only. Since pralatrexate is cytotoxic, used vials will be destroyed per institution, local, and all applicable policies and procedures. After study conclusion, all unused vials of pralatrexate may be destroyed at the site, following verification of accountability by an Allos representative.

### **16.3 Protocol Compliance**

The investigator is responsible for ensuring the study is conducted in accordance with the procedures and evaluations described in this protocol.

### **16.4 Sponsor Responsibilities**

#### **16.4.1 Amendments to the Protocol**

Any amendment to the protocol, as deemed appropriate by Allos, will be implemented as the study progresses. Allos may also make such changes to the protocol, as it deems necessary for safety reasons, or as may be required by the regulatory authorities. Amendments will be submitted to the IRB/EC/REB for written approval, before implementation. The expedited review procedure for an amendment is appropriate only if minor changes are made in the protocol.

#### **16.4.2 Safety Monitoring**

The clinical drug safety of pralatrexate will be continuously evaluated by the Study Medical Monitor on an ongoing basis during the course of this clinical study. All SAEs for pralatrexate in this study and all other ongoing clinical studies with pralatrexate will be processed in compliance with current regulatory guidelines by the Allos Clinical Drug Safety and Pharmacovigilance group. This processing will include a formal assessment of each SAE by the physician medical monitor for clinical drug safety. In addition, a cumulative review of all SAEs from all sources will be assessed on a bimonthly basis for change in frequency and severity of the SAEs by the physician medical monitor for clinical drug safety as a signal detection/trend evaluation.

## **16.5 Joint Investigator/Sponsor Responsibilities**

### **16.5.1 Access to Information for Monitoring and Auditing**

In accordance with ICH GCP guidelines and 21 CFR 312, the CRA/auditor must have direct access to the patient's source documentation in order to verify the data recorded in the CRFs. The CRA is responsible for routine review of the CRFs at regular intervals throughout the study and to verify adherence to the protocol, as well as the completeness, consistency, and accuracy of the data being recorded. The CRA/auditor must have access to any patient records needed to verify the entries on the CRFs. The investigator agrees to cooperate with the monitor to ensure that any problems detected in the course of these monitoring/auditing visits are resolved.

### **16.5.2 Termination of the Study**

For reasonable cause, either the investigator or the sponsor, Allos, may terminate the investigator's participation in this study, provided a written notice is submitted within the time period provided for in the Clinical Trial Agreement (CTA). In addition, Allos may terminate the study at any time upon immediate notice for any reason, including but not limited to, Allos' belief that termination is necessary for the safety of patients.

### **16.5.3 Publication Policy**

Allos recognizes the importance of communication of medical study data, and encourages the publication of such data in reputable scientific journals and the presentation of such data at scientific seminars and conferences. Any proposed publication or presentation of the data generated from the study must be provided to Allos for timely review in accordance with the terms of the CTA between the investigator, the institution, and Allos. Allos shall not, in its scientific publications or promotional material, quote from publications by investigators without full acknowledgment of the source. Criteria for inclusion in authorship in any publications resulting from the study will be determined and communicated in writing to all participating principal investigators.

## **16.6 Confidentiality**

All information provided to the investigator by Allos, including nonclinical data, protocols, CRFs, and verbal and written information, will be kept strictly confidential and confined to the clinical personnel involved in conducting this study, and no disclosure shall be made except in accordance with any right of publication granted to the investigator. All personnel will handle patient data in a confidential manner in accordance with applicable regulations governing clinical research. Upon request by a regulatory authority such as the US FDA and other regulatory authorities worldwide, the investigator/institution must make available for direct access all requested study-related records or reports generated as a result of a patient's participation in this study. This information may be related in confidence to the IRB/EC/REB or other committee functioning in a similar capacity. In addition, no reports or information about the study or its progress will be provided to anyone not involved in the study other than to Allos, or in confidence to the IRB/EC/REB or similar committee, except if required by law.

## Appendix 1 Schedule of Study Procedures/Evaluations Table for Pralatrexate Treatment

Visit	SCREENING	CYCLE 1		SUBSEQUENT CYCLES	RESPONSE	FOLLOW-UP		
	Within 21 Days Prior to Randomization	Dose 1	Doses 2-3	Cycle X, Dose X	At 8 (± 1) Weeks Post Randomization, Every 12 (± 1) Weeks Thereafter 	Initial Follow-up	Post-treatment Follow-up	Long-term FU
Informed consent  , Eligibility  , Medical/surgical history	X							
Confirmation of diagnosis by independent pathology review	X 							
B symptoms (> 38°C, night sweats, loss > 10% of body weight)	X	X		X 				
IPI score	X 							
CHOP-based chemotherapy	X 							
CT scan (chest, neck, abdomen, pelvis)  ; Whole-body PET  ; Medical photography 	X				X		X	
Bone marrow biopsy/aspirate	X 				X 		X 	
ECG	X							
Physical examination	X				X	X	X	
ECOG Performance Status (see Appendix 3)	X					X		
Hematology  /Chemistry  /Serum β-hCG pregnancy test 	X	X 	X 	X 		X		
Vitamin B 12 	X	X	X	X				
Folic acid 	X	X	X	X		X		
Concomitant medications		X	X	X		X 		
Adverse events	X	X	X	X		X 	X 	
Height, weight, BSA		X 		X 				
Pralatrexate Injection  and pharmacokinetics 		X 	X	X 				
Response assessment					X 		X 	
Reason for discontinuation of pralatrexate						X		
Subsequent therapy						X	X	X
Survival status								X

First response evaluation is 8 weeks (± 1 week) after randomization; see Section 10.6 for timing of response. Can be obtained prior to the screening period in order for confirmation of pathology prior to randomization. Prior to start of each new cycle. Document IPI score at initial diagnosis. Document dates, best response and post-CHOP response. Sections 10.1 and 10.6. Section 10.1. Section 10.6. Section 12.1. For females who are not postmenopausal or surgically sterile; perform within 14 days prior to randomization. Section 10.4. Section 7.1. Through 30 days after the last pralatrexate dose. From 31 days after the last dose of pralatrexate, only record pralatrexate-related AEs and attribution. Section 10.3.1. Collect sample for PK (Section 12.2.1). Tumor biopsy may be performed if needed to confirm response, per investigator decision. Document investigator's assessment of response.

## Appendix 2 Schedule of Study Procedures/Evaluations Table for Observation

Visit	SCREENING	BASELINE VISIT	SUBSEQUENT ASSESSMENTS		RESPONSE	FOLLOW-UP		
	Within 21 Days Prior to Randomization	Within 3 Days Following Randomization	Patient Contact Week 2 of 4-week Period	Clinic Visit Every 28 (± 3) Days	At 8 (± 1) Weeks Post Randomization, Every 12 (± 1) Weeks Thereafter 	Initial FU	Post-treatment FU/ Response Evaluation	Long-term FU
Informed consent  , Eligibility  , Medical/surgical history	X							
Confirmation of diagnosis by independent pathology review	X 							
B symptoms (> 38°C, night sweats, loss > 10% of body weight)	X	X		X				
IPI score	X 							
CHOP-based chemotherapy	X 							
CT scan (chest, neck, abdomen, pelvis)  ; Whole-body PET  ; Medical photography 	X				X		X	
Bone marrow biopsy/aspirate	X 				X 		X 	
ECG	X							
Physical examination	X				X	X	X	
ECOG Performance Status (see Appendix 3)	X					X		
Hematology  /Chemistry  /Serum β-hCG Pregnancy Test 	X	X 		X 		X		
Vitamin B 12 	X	X		X				
Folic acid 	X	X		X		X 		
Concomitant medications		X		X		X 		
Adverse events	X	X	X	X		X 		
Height and weight		X 						
Response assessment					X 		X 	
Reason for discontinuation of observation						X		
Subsequent therapy						X	X	X
Survival status								X

First response evaluation is 8 weeks (± 1 week) after randomization; see Section 10.6 for timing of response. Can be obtained prior to the screening period in order for confirmation of pathology prior to randomization. Document IPI score at initial diagnosis. Document dates, best response and post-CHOP response. Sections 10.1 and 10.6. Section 10.1. Section 10.6. Section 12.1. For females who are not postmenopausal or surgically sterile; perform within 14 days prior to randomization. Section 10.5. Section 7.1. Until treatment discontinuation criteria are met for patients in the Observation Arm. Tumor biopsy may be performed, if needed to confirm response, per investigator decision.

---

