### 7.3 Study Duration

Patients will receive study treatment (pralatrexate or observation) until one of the criteria listed below for study treatment discontinuation applies:

- Development of PD
- Initiation of radiation therapy (RT) or systemic chemo/biological therapy for treatment of PTCL
- Receipt of systemic steroids for > 10 days, with the exception of those as stated in exclusion criterion #5 (see [Section 8.4](#))
- Development of an AE that interferes with the patient's participation
- Lost to follow-up
- Patient decision
- Investigator decision
- Sponsor decision

In addition, for those patients randomized to the Pralatrexate Arm, additional pralatrexate treatment discontinuation criteria are:

- 3 or more consecutive doses of pralatrexate omitted or more than 28 days between doses of pralatrexate
- Treatment with pralatrexate for 2 years

All patients who receive at least 1 dose of pralatrexate will be followed for safety through 35 ( $\pm$  5) days after their last dose of pralatrexate or until all treatment-related AEs have resolved or returned to baseline/Grade 1, whichever is longer, or until it is determined that the outcome will not change with further follow-up.

Patients who are randomized to the Observation Arm who do not discontinue the study within 3 days of randomization will be followed for safety until 35 ( $\pm$  5) days after study treatment discontinuation criteria are met.

All patients who are randomized will be followed until objectively documented PD for up to 7 years from randomization. The details of response follow-up are provided in [Section 10.8](#). PD will be confirmed by central review until the first PFS analysis, see [Section 15.6.1](#), and per investigator assessment thereafter. Subsequent therapies for PTCL will be collected for up to 7 years from randomization; the best response to the first subsequent therapy will be collected. Survival follow-up will continue for up to 7 years from randomization.

As discussed in [Section 15.6.1](#), an analysis will be performed when both 280 PFS events and 128 OS events have occurred. If the PFS analysis is not significant at the 0.05 level, the study will be stopped.

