### 10.7.2 Observation Arm

Patients who are randomized to the Observation Arm will attend the Initial Follow-up Visit 35 days ( $\pm$  5 days) after study treatment discontinuation criteria are met.

In the event the patient withdraws consent to any further study participation and refuses to attend the Initial Follow-up Visit, the following procedures and evaluations must be performed at the time the patient withdraws consent.

1. Record concomitant medications through 30 days after study treatment discontinuation criteria ([Section 11.1](#)) are met.
2. Record all AEs and attribution (see <http://ctep.cancer.gov/reporting/ctc.html>) through 30 days after study treatment discontinuation criteria ([Section 11.1](#)) are met.
3. Assess and record B symptoms.

4. Perform physical examination. Document any new or worsened findings as AEs.
5. Assess and record ECOG performance status (see [Appendix 3](#)).
6. Local laboratory: collect blood for hematology and serum chemistry (including LDH, see [Section 12.1](#))
7. Review dosing of folic acid and document compliance.
8. Instruct patient to discontinue folic acid and vitamin B12.
9. Record reason for discontinuation of observation ([Section 11.1](#)).
10. Record first subsequent therapy for PTCL, if applicable. First subsequent therapy for PTCL is at the investigator's discretion and can include pralatrexate.

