### 14.3 Recording of Adverse Events

#### 14.3.1 Recording of Adverse Events

Any AE that occurs from the time the study IC is obtained until randomization needs to be recorded on the AE CRF page(s), **only** if the event was related to a study procedure. All other AEs/findings prior to randomization must be recorded as baseline findings on the applicable CRF page(s).

Any AE that occurs from randomization through 30 days after the last dose of pralatrexate or through 30 days after treatment discontinuation criteria are met for the Observation Arm must be recorded on the AE CRF. From 31 days after the last dose of pralatrexate, only AEs that are related to pralatrexate need to be captured on the AE CRF.

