### **14.6.2 Serious Adverse Event Reporting**

- Any SAE that occurs from the time the study IC is obtained until randomization needs to be reported only if the event was related to a study procedure.
- Any SAE that occurs from randomization through 30 days after the last dose of pralatrexate or through 30 days after treatment discontinuation criteria are met for the Observation Arm must be reported to Allos within 24 hours of knowledge of the event. From 31 days after the last dose of pralatrexate, patients will continue to be assessed for SAEs that are related to pralatrexate.

- SAEs (regardless of causality) must be reported and the SAER faxed **within 24 hours of knowledge of the event to:**

Allos Therapeutics, Inc.  
Primary Contact: Clinical Drug Safety and  
Pharmacovigilance Department  
Phone: [REDACTED]  
Fax: [REDACTED] or [REDACTED]  
Email: [contact]

Allos may request additional information from the investigator to ensure the timely completion of accurate safety reports. Safety data that are critical to the reportability of an SAE, such as causality assessment and serious criteria, should be included in the initial fax for SAER. If omitted, a timely response to drug safety data queries received from Allos or an Allos designee is expected.

The investigator must take all therapeutic measures necessary for resolution of the SAE. Any medications necessary for treatment of the SAE must be recorded onto the concomitant medication section of the patient's CRF.

SAEs that are pralatrexate-related will be followed until resolution or returned to baseline/Grade 1, whichever is longer, or until it is determined that the outcome will not change with further follow-up.

Additionally, the SAE must be entered on the AE page(s) of the CRF. Follow-up SAERs need to be submitted to Allos as soon as additional information regarding the event becomes available (eg, diagnosis is made, laboratory or test results, event course, outcome, etc). The Allos CRA or designee will collect the original SAER from the site.

Allos/designee will be responsible for reporting SAEs to the regulatory authorities in accordance with applicable expedited reporting regulatory guidelines. The investigator is responsible for submitting SAEs to his/her Institutional Review Board (IRB)/Ethics Committee (EC)/Research Ethics Board (REB).

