ECOG Performance Status – Safety Analysis Set	Summary of ECOG performance status results at each scheduled time-point and the change from baseline.
Concomitant Medications – Safety Analysis Set	Summary of administered concomitant medications by ATC code and preferred term.

FAS = full analysis set HR = hazard ratio SOC = system organ class
PFS = progression-free survival K-M = Kaplan Meier SAE = serious adverse event
OS = overall survival ORR = objective response rate ATC = Anatomical Therapeutic Chemical
CI = confidence interval AE = adverse event ECOG = Eastern Cooperative Oncology Group

Table 9.2. Planned Listings

Title	Description
Patient Accountability	Listing of all patients and the analysis set inclusion information.
Patient Withdrawal	Listing of all patients who withdraw from the study, including the reason for withdrawal and the time of withdrawal.
Protocol-specified Treatment Administration	Listing of all patient protocol-specified treatment administration information.
Adverse Events	Listing of all reported AEs by patient.
Serious Adverse Events	Listing of all patients with at least 1 reported SAE. Only the AEs identified as serious will be included. Listing will include patient number, SOC, and preferred term of AE, date of onset, date of resolution, CTCAE Grade, action taken, and outcome.
Deaths – Safety Analysis Set	Listing of deaths that occur within 30 days of the last dose of protocol specified treatment, including cause of death.
Adverse Events Leading to Protocol-specified Treatment Discontinuation	Listing of all patients who discontinue protocol-specified treatment due to an AE. The listing will include the AE, date of onset of the AE, date of resolution of the AE, severity of AE, and the CTCAE severity grade of the AE.
Hematology	Listing of all hematology parameters.
Serum Chemistry	Listing of all serum chemistry parameters.
Electrocardiograms	Listing of all ECG results, including heart rate, QRS, PR, QT, and QT _c intervals.
Concomitant Medications	Listing of all concomitant medications including the ATC code and preferred term.
ECOG Performance Status	Listing of ECOG performance status at each assessment.
Lesion Measurements	Listing of all lesions at each time-point, including the sum of all target lesions and change from baseline and percent change from baseline.
Efficacy Parameters	Listing of all efficacy parameters for each patient, including survival time, objective response, and PFS time.

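### Protocol Appendix 2 footnote 12 gives the Observation Arm no AE recording window after discontinuation, against 30 days in the protocol body and in the Pralatrexate Arm schedule

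*Protocol*

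**What the plan says.** **Observation Arm schedule.** Protocol Appendix 2 attaches footnote 12 to the adverse event, concomitant medication and folic acid cells of the Initial Follow-up column. The footnote reads "Until treatment discontinuation criteria are met for patients in the Observation Arm".

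**Protocol body, same arm.**
- Section 10.7.2 has AEs and concomitant medications recorded "through 30 days after study treatment discontinuation criteria" are met.
- Section 13 gives the same 30 days for concomitant medications.
- Section 14.3.1 says AEs from randomization "through 30 days after treatment discontinuation criteria are met for the Observation Arm must be recorded on the AE CRF".
- Section 14.6.2 says SAEs "through 30 days after treatment discontinuation criteria are met for the Observation Arm must be reported to Allos within 24 hours".
- Section 7.3 sets a safety follow-up period of 35 (± 5) days, counted from the day the criteria are met. SAP Section 3 gives the same period.

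**Pralatrexate Arm schedule.** Appendix 1 footnote 13 reads "Through 30 days after the last pralatrexate dose". Footnote 14 adds "From 31 days after the last dose of pralatrexate, only record pralatrexate-related AEs and attribution".

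**SAP.** Section 5.2 gives a treatment-emergent AE a start (study day 1) but no end. Table 9.2 plans, for the Safety Analysis Set, a "Listing of deaths that occur within 30 days of the last dose of protocol specified treatment, including cause of death".

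**The concern.** Taken at face value, the two schedule tables give the arms different AE collection periods: 30 days after the last dose on pralatrexate, and nothing after the discontinuation criteria are met on observation. Safety is the trial's secondary objective and the trial is open-label, so unequal ascertainment goes straight into a planned comparison. Fewer recorded control-arm AEs would make pralatrexate look relatively more toxic.

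The Table 9.2 death listing has a related gap. It covers a set that includes Observation patients, but it counts from a last dose that is not defined for them.

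**Working it through.** The plan states no figure on this point to reproduce. The main check is a comparison of texts, followed by an illustration of scale.

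**Step 1. Recording after the end of treatment or observation**

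| Source | Observation Arm | Pralatrexate Arm |
|---|---|---|
| Appendix 2 fn 12 / Appendix 1 fn 13 | 0 days | 30 days after last dose |
| Sections 10.7.2 / 10.7.1 (AEs, medications) | 30 days | 30 days after last dose |
| Section 13 (medications) | 30 days | 30 days after last dose |
| Section 14.3.1 (AEs) | 30 days | 30 days after last dose |
| Section 14.6.2 (SAEs) | 30 days | 30 days after last dose |

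Only the Appendix 2 entry departs from 30 days.

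**Step 2. Footnote 12 against its own table.** The column it annotates is a visit 30 to 40 days after the criteria are met (35 ± 5, Section 10.7.2). If recording ends on the day they are met, the AE cell at that visit covers none of the time since then.

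**Step 3. Does anything else settle it?** Section 10 says the appendices summarize the procedures, but no text states an order of precedence. On the SAP side, the treatment-emergent definition has no end date. The post-treatment variable in Section 11.3 depends on a treatment stop day that is not defined for observation, and no cutoff length is given. The analysis therefore does not equalise the arms, and whatever is collected enters the AE tables.

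**Step 4. Scale, as a ceiling.** Inputs:
- 183 Observation patients and an exponential control median PFS of 10 months (SAP Section 3.2).
- Observation visits for at most 24 months (Protocol Sections 10.5.2 and 10.5.3; SAP Section 3).
- Assumptions: observation ends only at a PFS event or at 24 months; every patient has a full 30-day tail; every site follows the footnote.

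Calculation:
- λ = ln 2 / 10 = 0.0693 per month.
- Mean observation = (1 − exp(−24λ)) / λ = (1 − 0.189) / 0.0693 = 11.7 months, or × 30.4375 = 356 days.
- Intended AE window = 356 + 30 = 386 days.
- Share lost = 30 / 386 = 7.8%, about 8%.
- In patient time: 183 × 30 = 5,490 patient-days; / 365.25 = 15.0 patient-years.

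**Step 5. Relaxing the full-tail assumption.** Section 11.1 lists no 2-year discontinuation criterion for the Observation Arm, so patients who reach 24 months event-free have no event that starts the 30-day clock.
- Share reaching 24 months = 2^(−2.4) = 0.189.
- Average tail = (1 − 0.189) × 30 = 24.3 days.
- Share lost = 24.3 / (356 + 24.3) = 6.4%.

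Patients whose PFS event is death have no tail either, which lowers it further. The documents do not split PFS events into deaths and progressions, so I put no number on that.

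**The case against.** The strongest reply is that this is a drafting slip. The body is uniform, Section 14.3.1 is worded as a requirement, and Appendix 2 itself marks AEs at a visit more than four weeks after the footnote's cutoff. The footnote may simply have lost a few words. That is probably right about intent, but it does not remove the conflict: the schedule is an operative part of the protocol and nothing ranks it below the body.

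Other parts of the reply limit how far the point goes:
- SAEs keep their own 30-day, 24-hour rule and must also be entered on the AE pages (Section 14.6.2). Section 10.7.2 also has new or worsened examination findings at the visit documented as AEs. The exposure is mainly non-serious AEs and concomitant medications.
- Section 14.2 sends sites to CRF completion guidelines, which are not among these documents. How sites would act is unknown.
- The arms are anchored differently even in the body (last dose against criteria met), so their windows would not be strictly identical after a dosing gap.

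A reader might infer that AEs cluster in the month after discontinuation and that the loss is therefore worse than its share of time. The documents give no data on this, and the point does not need it.

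A reader might also infer that the Table 9.2 listing would contain no Observation Arm deaths. The documents do not support that. The SAP does not define protocol-specified treatment, both arms receive vitamins under the protocol, and the protocol counts observation as study treatment. The listing is ambiguous for that arm, not shown to be empty. Section 9 presents these outputs as ones that could be provided. SAP Section 8.6 separately plans a deaths table, and listings and/or narratives of deaths that identify those before the end of safety follow-up, a period that is defined for observation.

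**Conclusion.** The inconsistency is real and stands in current text. Footnote 12 ends Observation Arm recording of AEs and concomitant medications 30 days earlier than Sections 10.7.2, 13 and 14.3.1 require, and the Pralatrexate Arm schedule has no such cut. The consequence is conditional: under-collection arises only where sites or CRFs follow the footnote. If it arises, it works against pralatrexate.

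The figure of about 8% should not be read as an expected loss. It needs universal adherence to the footnote and a full tail in every patient. It falls to about 6.4% without those who reach 2 years event-free, and lower again without those who die. It also assumes that observation ends only at a PFS event or 2 years; earlier exits for other reasons would shorten the denominator and raise the share.

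The death listing is a secondary wording gap in one SAP output. It should be corrected, but no death goes unreported because of it. Overall this should be fixed; it does not threaten the primary analyses.

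**What to change.** 1. **Appendix 2 footnote 12, AE and concomitant medication cells.** Replace the text with the Section 10.7.2 window, "through 30 days after study treatment discontinuation criteria" are met. This matches Sections 13 and 14.3.1.
2. **Folic acid cell.** Footnote 12 and Sections 7.1 and 10.7.2 must be reconciled. Which rule is right is a clinical matter and is not proposed here.
3. **SAP Table 9.2 death listing.** Keep the existing anchor and add, for the Observation Arm, deaths within 30 days of meeting the discontinuation criteria.
4. **SAP Section 5.2.** State one end to the AE analysis window for each arm, so that the incidence tables do not depend on which text a site followed. The anchor for Observation patients who complete 2 years also needs stating, because Section 11.1 provides none.

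The cost is one footnote, one listing definition and a sentence or two in the SAP. No visits are added, and the body of the protocol already requires the 30-day data wherever discontinuation criteria are met.
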